5.2.2 Baseline medical conditions

Medical conditions present at the screening visit, that do not worsen in severity or frequency during the study are defined as baseline medical conditions and are not AEs. These medical conditions should be adequately documented on the appropriate page of the CRF, i.e. the medical history page. However, medical conditions present at the initial study visit that worsen in severity or frequency during the study should be recorded and reported as AEs.

5.3 SAE Reporting

Any SAE, including death from any cause that occurs after a patient has signed the Informed Consent and up to any follow-up visit performed to monitor any drug-related AE that is still ongoing beyond the last scheduled visit until recovery (regardless of relationship to study drug) must be reported by the Investigators to Italfarmaco S.p.A. within 24 hours of learning of its occurrence.

Related SAEs **MUST** be collected and reported regardless of the time elapsed from the last study drug administration, even if the study has been closed. Anyway, no active subject monitoring by the Investigators is required.

The Investigators are required to complete the SAE Form, according with the procedures described in the study manual and within 24 hours of learning of its occurrence. Sufficient details must be provided to allow for a complete medical assessment of the AE and independent determination of possible causality. The Investigators are obliged to pursue and provide additional information as requested by Italfarmaco S.p.A. or their designee(s).

The Investigator must notify the SAE to the Drug Safety Unit (hereinafter “DSU”) of Italfarmaco S.p.A. by sending the SAE Form, according with the procedures indicated in the study manual and within 24 hours of learning of its occurrence.

The details of the DSU are specified here below:

Italfarmaco S.p.A.

***Drug Safety Unit [name]
[name]***

Phone: PPD [redacted]

Fax: PPD [redacted]

Fax (back-up): PPD [redacted]

Mobile: PPD [redacted] ***e-mail:*** PPD [redacted]

The same procedure must be applied to the SAE follow-up information.

All serious and unexpected AE that are associated with the use of the study drug (SUSARs) will be notified by Italfarmaco S.p.A. DSU to the competent authority within the required time and following procedures required by applicable laws. It is imperative that Italfarmaco S.p.A. be informed as soon as possible, so that reporting can be done within the required time frame.

The SAEs will also be recorded in the dedicated AE section of the CRF.

5.3.1 Over-dosage and other situations putting the patient at risk of adverse reaction

In general, a drug overdose in a clinical trial is defined as the accidental or intentional use of a drug or medicine in an amount exceeding the protocol defined dose(s). In this study, if an AE is associated with (“results from”) the overdose of Givinostat, the AE is reported as a SAE, even if no other criteria for seriousness are met.

If a dose of Givinostat meeting the protocol definition of overdose is taken without any associated clinical symptoms or abnormal laboratory results, the overdose is reported as a non-serious Event of Clinical Interest (ECI), using the terminology “accidental or intentional overdose without adverse effect.” Any instance of overdose (suspected or confirmed, with and without an AE) must be reported to the sponsor within 24 hours and, only in case of AEs, it must be fully documented as a SAE. Details of any signs or symptoms and their management should be recorded in the SAE Form including details of any antidote(s) or systematic treatment administered. Any signs or symptoms of over-dosage will be treated symptomatically.

Any other situations putting the patient at risk of adverse reaction, such as misuse and abuse, medication errors, suspect of transmission of infective agents must be reported to the sponsor within 24 hours and must be fully documented as a SAE.

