5.1.4 Serious Adverse Event (SAE)

A Serious Adverse Event (experience) or reaction is “any untoward medical occurrence that at any dose:

- results is fatal (results in the outcome death);
- is life-threatening*;
- required in-patient hospitalisation or prolongation of existing hospitalisation;
- results in persistent or significant disability/incapacity;
- is a congenital anomaly/birth defect;
- is medically significant or requires intervention to prevent one or other of the outcomes listed above;
- consists in the transmission of an infective agent through the IMP.”

**The term life-threatening refers to an event in which the patient is at risk of death at the time of the event; it does not refer to an event which hypothetically may cause death if it is more severe.*

Medical judgement should be exercised in deciding whether an adverse event/reaction is serious in other situations. Important adverse events/ reactions that are not immediately life-threatening or do not result in death or hospitalisation but may jeopardise the subject or may require intervention to prevent one of the other outcomes listed in the definition above, should also be considered serious.

The pre-planned hospitalization or adverse reaction expected as part of the trial treatment (e.g. standard expected side effect of chemotherapy) should not be considered as SAE.

A Suspected Unexpected Serious Adverse Reaction (SUSAR) is referred to an adverse drug reaction which complies with both the definitions of “serious” and “unexpected”.

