AEs will be coded using MedDRA dictionary (using the most updated version). Adverse events (AEs) will be reported on a per subject basis. If a patient has more than one AE for a treatment that coded to the same preferred term (PT), the patient will be counted only once for that preferred term. Similarly, if a patient has more than one AE for a treatment within a system organ class (SOC) category, the patient will be counted only once in that system organ class category. A patient with multiple CTCAE grades for an AE will be summarized under the maximum CTCAE grade recorded for the event.

Any Adverse Events which started at or after the first administration of study treatment will be considered a treatment Emergent Adverse Event (TEAE). If the start date is missing for an AE, the AE will be considered to be treatment emergent.

TEAE included in this analysis are defined as those starting prior to the date of the first administration of Cycle 4 and include those started prior but continued during the subsequent cycle.

An overview of AEs including the number of subjects with at least one AE, at least one TEAE, at least one drug-related TEAE, at least one serious TEAE, any SAE, any AE leading to death, any TEAE leading to death, any TEAE leading to drug discontinuation, at least one grade ≥ 3 TEAE, will be presented. The following AE frequency tables will be also provided:

- incidence of TEAEs by primary SOC and PT;
- incidence of drug-related TEAEs by primary SOC and PT;
- incidence of TEAEs by maximum severity, primary SOC and PT;
- incidence of TEAEs by strongest relationship, maximum severity, primary SOC and PT;
- incidence of TESAEs by primary SOC and PT;
- incidence of TEAEs leading to study drug discontinuation by primary SOC and PT;
- incidence of TEAEs leading to dose modification by primary SOC and PT.

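### Section 5.3.1 makes an overdose without an adverse event non-serious, but has at-risk misuse and medication errors documented as SAEs with no adverse event required

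*Protocol*

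**What the plan says.** Protocol section 5.1.4 defines an SAE mainly by outcome or medical importance. Its criteria include death, threat to life and "required in-patient hospitalisation or prolongation of existing hospitalisation". It also covers medically significant events and transmission of an infective agent through the study drug, and it allows medical judgement for other important adverse events. It does not mention overdose, misuse, abuse or medication error.

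Section 5.3.1 then sets three rules:

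- **Overdose with an adverse event:** "the AE is reported as a SAE, even if no other criteria for seriousness are met".
- **Overdose without one:** if the dose "is taken without any associated clinical symptoms or abnormal laboratory results", it is a non-serious event of clinical interest. The sponsor must still be told within 24 hours, but "only in case of AEs, it must be fully documented as a SAE".
- **Everything else:** "Any other situations putting the patient at risk of adverse reaction, such as misuse and abuse, medication errors" and suspected transmission of an infective agent must be reported "within 24 hours and must be fully documented as a SAE".

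Section 5.3 has SAEs entered in the AE section of the CRF as well. In section 6.2.5.2 the Part B safety overview counts patients with a serious treatment-emergent event and patients with any SAE, and a table of "incidence of TESAEs by primary SOC and PT" is planned.

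**The concern.** The second and third rules use different tests for the same kind of problem. For an overdose, SAE status depends on whether an adverse event followed. For misuse, abuse or a medication error it depends only on whether the patient was put at risk. Neither 5.1.4 nor 5.3.1 gives a reason for the difference.

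What is at stake is the meaning of the SAE counts. A record that is an SAE only because of the last paragraph of 5.3.1 would stand in the same tables as a hospitalisation or a life-threatening event. Sites could also read that paragraph differently, so the same error might be an SAE at one site and not at another. Part B patients take the drug themselves at home, three capsule strengths are supplied, and doses can be reduced and raised again, so handling errors are plausible.

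**Working it through.** The plan gives no figure to reproduce. The check is a comparison of the rules, followed by one division.

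**1. The rules of 5.3.1 side by side**

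| Situation | Adverse event required for SAE status? | Class under 5.3.1 | Listed in 5.1.4? |
|---|---|---|---|
| Overdose, no symptom or abnormal laboratory result | Yes, and absent | Non-serious event of clinical interest | No |
| Overdose with an adverse event | Yes, and present | SAE whatever the outcome | No |
| Misuse, abuse or medication error that puts the patient at risk | No condition stated | Documented as an SAE | No |

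Rows 1 and 3 conflict in principle: neither patient need have been harmed, yet one record is non-serious and the other is an SAE.

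**2. Whether 5.1.4 resolves the conflict.** It does not. Its judgement clause extends seriousness to important adverse events or reactions, so an event must exist. A no-harm error is not brought in by that route. Suspected transmission of an infective agent is a separate case, because 5.1.4 already lists actual transmission. It is not part of this point.

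**3. Whether the records reach the tables**

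- Section 5.3: SAEs go into the AE section of the CRF.
- Section 5.2: seriousness is recorded for each event, but the criterion that was met is not among the required items. An analyst may be unable to separate the two kinds of SAE later.
- Section 6.2.5.2: the any-SAE line has no further filter. The treatment-emergent tables require an adverse event that began at or after the first dose, and section 5.1.1 defines an adverse event as an untoward medical occurrence. A no-harm error fits that definition poorly. The route into the any-SAE line is therefore plainer than the route into the treatment-emergent tables, but nothing in the protocol closes either.

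**4. Size per patient.** The input is the planned Part B size of 28 (Synopsis, number of patients; section 6.3). For one patient whose only SAE arises from the last paragraph of 5.3.1:

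change in crude SAE incidence = 1/28 = 0.036, or 3.6 percentage points.

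The total effect is 3.6 points times the number of such patients. The documents do not give that number.

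**The case against.** The strongest reply is that documenting something as an SAE may mean only using the SAE Form and the 24-hour route, since 5.3.1 sits under SAE reporting. That reading is possible. However, the section does not say so, and it uses the same phrase for an overdose with an adverse event, which it states is reported as an SAE. The ambiguity stands, and it is itself a reason to clarify.

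A second reply is that handling of these records belongs in the analysis plan or the study manual. Layout of tables does. Classification by the investigator does not, and that is where the inconsistency lies.

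Several stronger conclusions are tempting, and the documents do not support them:

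- A reader might infer that every harmless error is an SAE, for example taking a lower strength than prescribed. The clause covers situations that put the patient at risk of an adverse reaction, and nothing says that under-dosing does. Missed doses and under-use are treated as dosing and compliance matters in sections 4.3.3.3 and 4.4.6.
- A reader might infer that 5.1.4 is purely outcome-based. It is not, as its medical-significance and infective-agent criteria show.
- A reader might call the rule for overdoses with an adverse event a mistake. It is an openly stated, conservative choice for this study. It also bears on SUSAR status, which requires seriousness, so removing it would be a trade-off and not a correction.
- A reader might state that SAE incidence is overstated, or put a percentage on the inflation. The protocol gives no error rate and no expected SAE rate.

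**Conclusion.** The inconsistency is real but minor. Within 5.3.1, an overdose without an adverse event is non-serious, while at-risk misuse, abuse and medication errors are documented as SAEs without one, and 5.1.4 does not list them. SAE counts can therefore include handling errors that caused no harm, at 3.6 points per affected patient in Part B.

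This rests on two conditions: that sites take the last paragraph of 5.3.1 literally, and that the resulting records enter the SAE tables, as sections 5.3 and 6.2.5.2 indicate. The overall effect may be small. The Part B safety endpoints in section 3.1 are framed around patients with adverse events and the nature, frequency and grade of related events. They do not name SAE incidence, and the two-stage decision uses responses only. What needs protecting is the descriptive SAE reporting.

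**What to change.** Reconcile the last paragraph of 5.3.1 with 5.1.4 and with the overdose rule:

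1. Keep 24-hour reporting to the sponsor and the SAE Form for misuse, abuse and medication errors.
2. Record those without an adverse event as non-serious special situations, in line with an overdose without one.
3. Classify them as serious in the CRF, and count them in the SAE and treatment-emergent SAE tables, only when an accompanying event meets 5.1.4.
4. Leave the study-specific rule for an adverse event resulting from an overdose, but flag those events so that the tables distinguish them from SAEs that meet 5.1.4.

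The cost is a protocol wording change and one flag in the CRF and safety database. Expedited reporting to the sponsor is not lost. Because the overdose rule stays, the seriousness of overdose-related events, and so their SUSAR status, does not change.

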5.3.2 Pregnancy

Female patients who have a positive pregnancy test during the pre-treatment evaluations assessment are not eligible for study participation. If a patient becomes pregnant while on study, the treatment shall be immediately stopped. The investigator is required to report the pregnancy to Italfarmaco S.p.A. DSU within 24 hours of learning of its occurrence via telephone and/or fax and/or mail (only in case the mail will be automatically generated by the e-CRF). If initially reported via telephone, this must be followed-up with a written report via fax and/or mail (only in case the mail will be automatically generated by the e-CRF) within 24 hours of the telephone report.

Patients should be instructed to notify the investigator if, after completion of the study, it is determined that they became pregnant during the treatment phase or through 3 months after the last dose of study drug.

Whenever possible, a pregnancy with an onset within the above defined time frame should be followed until termination, any premature termination should be reported, and the status of the mother and child should be reported to the sponsor after delivery.

If the Investigator is made aware that the partner of a male patient who is participating to the study become pregnant, he/she is required to report the pregnancy to Italfarmaco S.p.A. DSU within 24 hours via telephone and/or fax and/or mail (only in case the mail will be automatically generated by the e-CRF). If initially reported via telephone, this

must be followed-up with a written report via fax and/or mail (only in case the mail will be automatically generated by the e-CRF) within 24 hours of the telephone report.

Whenever possible, such pregnancy should be followed until termination, any premature termination should be reported, and the status of the mother and child should be reported to the sponsor after delivery.

6. STATISTICAL METHODS

6.1 Experimental design

Two-part, multicenter, open label, non-randomized, phase Ib/II study.

6.2 Statistical methods to be employed

Methods here represent the outline of the intended methods.

A Statistical Analysis Plan (SAP) will be produced before the database lock and will contain full details of all planned summaries, listings and analyses.

A standard 3+3 design adopting a modified Fibonacci escalation schema will be used in **Part A** [25, 26, 27].

Sample size for **Part B** was discussed for the primary end point defined as the Overall Response Rate after 3 cycles. Simon's 2-stage design will be employed in **Part B** [30] with the aim of testing the "null hypothesis" that $RR \leq 0.50$ versus the "alternative" that $RR \geq 0.75$. Response rate will be assessed as defined in [paragraph 6.2.5.2](#). Overall up to 28 patients will need to be recruited, 12 patients being enrolled in Stage-1. PV patients enrolled at the MTD in **Part A** may be counted towards Stage 1. Under the "null hypothesis" (if $RR = 0.50$), the expected total sample size is of 18.2 patients, the probability of early termination at the end of Stage-1 is 0.613 and the probability of rejecting the "null hypothesis" is 0.081 (the target for the type-I error being 0.100). Under the "alternative hypothesis" (if $RR = 0.75$), the probability of rejecting the "null hypothesis" in favour of the "alternative" is 0.902 (the type-II error being 0.098). After testing the treatment on 12 patients in Stage-1, if 6 or fewer patients respond to the treatment the trial will be terminated rejecting the "alternative" that $RR \geq 0.75$. Otherwise, the trial goes on to Stage-2 enrolling further 16 patients to a total of 28 patients. If at the end of Stage-2, a total of 17 or fewer patients respond to the treatment the "alternative hypothesis" that $RR \geq 0.75$ will be rejected; alternatively, if 18 or more patients respond, the "null hypothesis" that $RR \leq 0.50$ will be rejected. Estimations are obtained from proprietary software (based on SAS ® 9.2) according to the algorithm proposed by R. Simon [30].

Summary statistics will be calculated for all variables. For each continuous variable, the mean, standard deviation, median, minimum value and maximum value will be computed. For each discrete variable the number of patients in each category with non-missing values in relation to all patients with non-missing values of that variable will be provided. Results will be displayed within each cohort and overall, where applicable.

Clinical Study Protocol
Version 3.0 – 29th July 2015

Statistical calculations will be carried-out by resorting to SAS version 9.2 (or later). Both continuous and categorical data will be summarized and tabulated in 2-way tables (variable-by-visit). The main purpose of this phase Ib/II study consists in providing accurate estimates of clinically relevant variables and measures. From the statistical viewpoint this translates in estimating confidence intervals (CIs) with adequate precision where precision represents the degree of uncertainty.

The two tailed 95% CIs of the sample estimates will be computed using parametric approaches if deemed appropriate. Otherwise the StatXact-4 software will be used in order to compute Exact/Nonparametric 95% CIs.

Sub-groups analyses will be performed mainly for exploratory purposes. Since these analyses will be used to promote hypothesis rather than confirm them, no adjustments for type I error inflation due to multiplicity of the tests will be considered. Moreover post-hoc and data-driven analyses will be carefully considered and ranked according to their biological plausibility.

6.2.1 Analysis Sets

The following analysis sets will be defined:

- Safety analysis set (SAF): The Safety analysis set will include all recruited patients who receive at least one dose of study medication. All safety analyses will be conducted on this population.
- Intent-to-treat analysis set (ITT): The Intent-to-treat analysis set will include all recruited patients who receive at least one dose of study medication and from whom at least one post-baseline efficacy measurement is obtained. All efficacy analyses will be conducted on this population and will be based on the *effective/actual* DL/daily doses of Givinostat at which each patient has been treated.
- Per Protocol analysis set (PP): In order to assess the robustness of the efficacy analysis, the analysis of the efficacy end-point could be repeated in the Per Protocol (PP) analysis set. The Per-protocol analysis set will include all ITT patients who receive at least 14 daily doses without interruptions, **and** without any major deviation from the protocol procedures.
- MTD analysis set: The MTD analysis set will include all patients who experienced DLTs in Cycle 1 of **Part A**, **or** who received at least 90% of the doses of study medication in Cycle 1 of **Part A**. The data regarding the Cycle 1 of **Part A** will be used to determine MTD from this analysis set.
- PK Analysis set: will consist of all SAF patients who with at least 1 PK assessment. This analysis set will be used for PK analysis.

The number and percentage of the patients included in the analysis populations will be reported in a table showing the reason of exclusion for all patients enrolled into study. A listing of reasons of exclusion from analysis population will be provided.

6.2.2 Background and demographic characteristics

Demographic data and other baseline characteristics, including medical history, will be analyzed based on safety population. Summary statistics will be provided for all collected variables. For continuous variables, the following statistics will be calculated: mean, standard deviation, median, minimum and maximum values. For discrete variables, the following statistics will be presented: number of patients with non missing values in each category in relation to all patients with non missing values of the respective variable.

Medical history will be listed by patient based on safety population.

6.2.3 IMP

The duration (days) of exposure of Givinostat will be calculated for each patient, and will be summarized descriptively including the mean, standard deviation, median, minimum and maximum.

In addition, the daily dosage (mg) of Givinostat will be summarized for each patient, and will be summarized descriptively including the mean, standard deviation, median, minimum and maximum.

Reason for treatment discontinuation and number of patients treated beyond protocol-specified discontinuation criteria will also be summarized. Analysis will be based on safety population.

6.2.4 Prior and Concomitant medications and prior and concomitant significant non-drug therapies

Prior medications and significant non-drug therapies (e.g. phlebotomies, transfusions) to treat PV will include regimens discontinued up to 24 weeks prior to enrolment. The information captured will include drug name, start and stop dates, best response to therapy (where applicable) and reason for discontinuations.

Prior medications and prior significant non-drug therapies are defined as those starting and ending prior to the first administration of investigational study drug. Concomitant medications and concomitant significant non-drug therapies are defined as those started at or after first administration of study drug and include those started prior to the first administration of investigational study drug but continued during the study.

Prior and concomitant medications will be classified according to active drug substance using the WHO-DRL drug dictionary (using the most updated version). Frequency tabulations will be presented for prior and concomitant medication by primary therapeutic subgroup (3rd level ATC code), and generic name. Frequency tabulations will be also presented for significant non-drug therapies.

All analyses will be based on safety population.

